## 6.0 SUBJECT WITHDRAWALS

Subjects may be withdrawn from the study for the following reasons:

- 1) Subject non-compliance with study procedures
- 2) Unacceptable adverse events (safety or tolerability)
- 3) The subject may withdraw from the study at any time and for any reason
- 4) Clinician decision that it is in the best interest of the subject to withdraw from the study

## 7.0 SAFETY AND REPORTABLE EVENTS

### 7.1 Adverse Event Definition

There is no additional risk as compared to standard risk with this equipment.

### 7.2 Non-Serious Adverse Event

- Dental damage
- Corneal Abrasion

### 7.3 Recording Adverse Events

All adverse events, whether observed by the Investigator, elicited from or volunteered by the subject, should be documented. Each adverse event will include a brief description of the experience, the date of onset, the date of resolution, the duration and type of experience, the severity, the relationship to investigational product (i.e., drug or device), contributing factors, and any action taken with respect to the study drug/device.

Investigators and research coordinators will be instructed that all AE and corresponding relevant information should be recorded on the Adverse Event Form. The Principal Investigator will be responsible for reporting AEs to the IRB of record in accordance with IRB procedures.

### 7.4 Responsibilities for Reporting Serious Adverse Events

The Principal Investigator will record all serious adverse experiences that occur during the study period in the appropriate source documents and/or AE log as applicable.

## 8.0 RISK/BENEFIT ASSESSMENT

### **8.1 Potential Risks**

There are no additional risks to the standard risk associated with intubation with this equipment.

### **8.2 Protection Against Risks**

Standard protocol will be followed, eye protection after induction of anesthesia; careful placement of equipment to prevent dental damage.

### **8.3 Potential Benefits to Subjects**

- Improved oxygen delivery, administration, and oxygenation
- Improve efficiency of tracheal intubation
- Reduce post-op respiratory complications

### **8.4 Alternatives to Participation**

Standard airway management procedures will be implemented.

## **9.0 CONFIDENTIALITY OF DATA AND INFORMATION STORAGE**

### **9.1 Institutional Review Board (IRB)**

Prior to participating in this investigation, the site will be required to obtain approval from its governing IRB. The Principal Investigator is responsible for obtaining and maintaining IRB approval to participate in this investigation. The IRB for this study is the institutional IRB at the University of Texas MD Anderson Cancer Center in Houston.

### **9.2 Subject Data Confidentiality**

Information about study subjects will be kept confidential and managed according to the requirements of the Health Insurance Portability and Accountability Act of 1996 (HIPAA). Patient data retrieved from the Case Report Forms (CRF's) or patients' electronic medical record will be entered into an online database (i.e. REDCap). PI will consider all information concerning a subject or their participation in this investigation as confidential. Only authorized study personnel will have access to these confidential files and have the right to inspect and copy all of the records pertinent to this study for data verification. This may include medical information gathered prior to the onset of the study. All data used in the analysis and reporting of this investigation will be conducted without identifiable reference to specific subject name. The site will maintain a list matching each subject's name with the study identification in OnCore.

To ensure compliance with the Health Insurance Portability and Accountability Act (HIPAA), all subjects enrolled in the study will be required to provide authorization to disclose Protected Health Information (PHI). This authorization will be included in the informed consent document as required by the IRB. In all study reports and in any resulting publications, their initials and/or study identification will not refer to the subjects.

## **10.0 SAMPLE SIZE DETERMINATION AND DATA ANALYSIS**

### **10.1 Sample Size Determination**

A total of 60 evaluable patients will be randomized to each intervention arm. With 60 patients per study arm, a 2-sided chi-square test with alpha = 0.05, and an assumed rate of difficult ETT in one

arm of 30% on the control arm, then a minimum detectable difficult ETT rate of 10% (an absolute difference of 20 percentage points) would be considered statistically significant (nQuery v7) with power of 80%. For each study arm consisting of 60 patients, estimated rates of difficult ETT will be provided using exact 95% CI using the method of Clopper-Pearson. For example, a rate of 25% would provide exact 95% confidence interval limits that do not exceed (0.15 0.38), exact 99% CI limits that do not exceed (0.12, 0.42) using the method of Clopper-Pearson.

In the pursuit of ensuring that a sufficient number of evaluable patients have been enrolled, an adjustment will be made to the total number of randomized patients by adding 20% or an additional 24 patients (12 per study arm). This modification will result in a total sample size of 144 patients. However, the accrual of participants will cease once 60 evaluable patients have been reached on each study arm.

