### 3.2 Inclusion and Exclusion Criteria

#### Inclusion Criteria:

- Ages  $\geq 18$  years of age
- All surgical patients with known or suspected difficult airways that meet at least three (3) of the Difficult Airway criteria [Mallampati III-IV, Neck circumference  $>$  or  $= 40$  cm, Sternomental distance  $< 12$  cm, Thyromental distance  $< 6$  cm, Mouth opening  $< 4$  cm, BMI  $\geq 35$  kg/m $^2$ , Upper Lip Bite Test - ULBT (class III)] or history of radiation to the head or neck area
- American Society of Anesthesiology (ASA) I-IV
- Has provided written informed consent

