##### Randomization

OnCore will be used to randomly assign eligible study participants to either the control group (N = 60) or the study (intervention) group (N = 60). Additionally, the collection of demographic information will take place before anesthetic and surgical care to acquire baseline data information on: age, gender, height, weight, and BMI. Patients will be randomized after consenting and enrolling into the trial, preoperatively, on their scheduled day of surgery.

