### **5.3 Measurements**

Morphometric characteristics and airway assessments of all patients will be recorded in the preoperative holding area. Patients will be asked questions to assess degree of irritation. Baseline measures of blood pressure, pulse, oxygen saturation, and End-Tidal CO2 will be recorded prior to induction. Vital signs will be recorded during preoxygenation, before induction of anesthesia, after induction of anesthesia, during laryngoscopy and/or bronchoscopy, after successful intubation, and 3 times while in recovery (at PACU arrival, at 30 and 60 minutes after PACU arrival). Lastly, we will ask the same questions to the patients about degree of irritation when they're fully awake. Additionally, the anesthesiologist will provide a personal, subjective assessment following successful or failed/rescue intubation with the corresponding research procedure/technique.

**Intubation technique:** Although the time required for successful intubation is not a primary endpoint for the study, the time and number of attempts required for successful tracheal intubation will be recorded for each patient. The glottis view obtained will be recorded using the percentage of glottis opening (POGO) score. If the epiglottis is down folded and a jaw lift is required to improve view, this information will be reported. The view both before and after jaw lift will also be recorded using the POGO score. If blood or secretions are present and require suctioning, time will be stopped while suctioning occurs and this will be recorded. If rotation of the ETT to obtain intubation is required or esophageal intubation occurs, this will also be recorded. The subjective level of difficulty in the performance of intubation will also be recorded.[2]

**Intubation:** We will record how long in seconds and number of attempts required for successful endotracheal intubation in each group. An attempt is defined as an attempt at placement of an ETT through the glottic opening, pass the vocal cords, and into the trachea. Removal/reinsertion of the laryngoscope/fiberoptic scope will constitute as a new attempt. If more than 2 attempts are needed or if the anesthesia provider discontinues protocol procedures, for any reason, the case will be deemed a failure.

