## **10.3 Exploratory Analyses**

Depending on the distributional assessment of outcomes for each of the 3 items: i) time of intubation, ii) number of attempts, and iii) the number of complications, a total score will be derived for each patient. Each outcome will be translated into a binary scale. For example, starting with intubation time, the completion a procedure within 60 seconds will be assigned a '0', and completion taking more than 60 seconds will assign a '1'. For the number of attempts, we will assign a '0' for a single attempt and a '1' for more than a single attempt. And finally for complications, we will assign a '0' for no complication arising and a '1' for any complications arising. The total score will range from 0 to 3 and will be summarized using frequencies and percentages related to each level of the total score and using the mean score and standard deviation, whichever is more appropriate. Other exploratory outcomes include: Ease of ETT insertion (ranked on a 1 to 5 scale as described in Section 5.4) and will be summarized using descriptive statistics. These exploratory study outcomes will be compared between treatment arms using an independent samples t-tests or chi-square tests. Potential cut-points for these exploratory outcomes may be considered to inform if low versus high scores are associated with select patient outcomes of interest. Cumulative incidence plots will be used to visualize time to intubation, if appropriate. Multiple logistic regression analyses will be conducted to assess the association between any dichotomous outcomes of interest and type of intervention after adjusting for select covariates of interest.

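### The primary test is a valid unadjusted chi-square; prespecified adjustment for baseline airway data already recorded could add about 0 to 6 points of power without extra patients

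*Combined protocol and SAP*

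**What the plan says.** - **Primary test.** Section 10.1 assumes "a 2-sided chi-square test with alpha = 0.05", with 60 evaluable patients per arm, 30% difficult placements on control and 10% on the combination, and 80% power. The Brief Analysis Plan in the summary table repeats this. No covariate is mentioned. The only intervals promised are Clopper-Pearson limits for each arm's own rate.
- **Planned analysis.** Section 10.2 covers only the secondary objective, so the chi-square in the sample-size text is all there is for the primary comparison.
- **Baseline data.** Section 5.3 states: "Morphometric characteristics and airway assessments of all patients will be recorded in the preoperative holding area". Under Section 3.2 a patient enters either by meeting at least three of seven difficult-airway criteria "or history of radiation to the head or neck area". Eligibility is verified before enrolment (Section 4.1), and randomisation follows enrolment (Section 5.1).
- **Allocation.** Section 5.1 assigns patients to "the control group (N = 60) or the study (intervention) group (N = 60"). It names no stratification factor.
- **Adjustment.** It appears only among the exploratory analyses (Section 10.3): "Multiple logistic regression analyses will be conducted to assess the association between any dichotomous outcomes of interest and type of intervention". Neither the outcomes nor the covariates are named.

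**The concern.** The trial measures, before randomisation, features that it treats as markers of a difficult airway, then leaves them out of its main comparison. Two entry routes make it plausible that baseline risk differs between patients, and no stratification balances that risk across arms. Few events are expected: 60 × 0.30 + 60 × 0.10 = 18 + 6 = 24. One event moves an arm's rate by 1/60, or 1.7 percentage points, so a modest chance imbalance in airway difficulty would show in the estimate. Adjustment for prognostic baseline variables would remove part of that noise.

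There is also a prespecification issue. The primary outcome is dichotomous, so the exploratory model can be applied to it. An adjusted odds ratio with covariates chosen after the data are seen could then stand beside the primary result.

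**Working it through.** **Step 1: reproduce the plan's power.** Inputs from Section 10.1: n = 60 per arm, p1 = 0.30, p2 = 0.10, two-sided alpha 0.05. The mean rate is 0.20.

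Pooled-variance formula: power = Φ{[|p1 − p2|√n − 1.960√(2 × 0.20 × 0.80)] / √(p1(1 − p1) + p2(1 − p2))}
= Φ{[0.2 × 7.746 − 1.960 × 0.5657] / √(0.21 + 0.09)}
= Φ{(1.549 − 1.109)/0.5477} = Φ(0.804) = 78.9%.

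The unpooled version gives Φ(0.2/√(0.30/60) − 1.960) = Φ(0.868) = 80.7%. Exact enumeration of the uncorrected chi-square gives 80.2%. The stated 80% therefore reproduces for the unadjusted, uncorrected test. With Yates' correction or Fisher's exact test it would be 73.0%.

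**Step 2: what a smaller standard error is worth.** If adjustment shrinks the standard error by a fraction s, power rises from 80% to Φ[(1.960 + 0.842)/(1 − s) − 1.960]:

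| s | Power |
|---|---|
| 0 | 80% |
| 2% | 81.6% |
| 5% | 83.9% |
| 8% | 86.1% |

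Equivalently, a covariate explaining a share R² of the outcome variance acts like an effective n of 60/(1 − R²) per arm. R² = 0.05 gives 63.2 and 81.0% power; R² = 0.15 gives 70.6 and 85.2%, against 78.9% at R² = 0 on the same formula. Since √(1 − 0.15) = 0.92, the 8% row corresponds to R² of about 0.15.

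**Step 3: simulate the two-covariate model under the trial's eligibility rule.** The covariates are the criteria count and radiation history (yes/no). The analysis is a logistic model standardised to a risk difference, with a robust variance and a t reference, at 60 per arm and 30% against 10%. The documents give no prognostic strength, so it is assumed over a range. In one fully stated setting (6,000 trials each), 40% of patients enter with prior radiation and counts of 0 to 5, and the rest have counts of 3 to 6:

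| Control-arm AUC (assumed) | Chi-square power | Adjusted power | Gain (points) |
|---|---|---|---|
| 0.50 | 79.4% | 79.4% | 0 |
| 0.62 | 80.6% | 81.9% | 1.3 |
| 0.67 | 79.4% | 82.5% | 3.1 |
| 0.72 | 80.2% | 85.7% | 5.5 |

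The Monte Carlo standard error of one power figure is √(0.8 × 0.2/6000) = 0.5 points. The model failed to converge in under 0.3% of trials. A further simulation of the same model and entry rule, with the small-sample correction, gave no gain at AUC 0.50, about 1.5 to 3 points at 0.61 to 0.68 and about 6 points at 0.75.

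**Step 4: type I error.** With the small-sample correction it was 5.1 to 5.6% adjusted, against 5.1 to 5.5% for the chi-square. Without the correction, a simulation under the same entry rule gave 5.3 to 6.2%, which is 0.4 to 0.8 points above the chi-square in every setting. The correction is therefore needed.

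**The case against.** The strongest reply is that nothing is broken. Randomisation makes the unadjusted chi-square valid, its alpha already allows for chance imbalance, and the trial was sized for it. That stands. A reader might infer that the plan loses power or that its primary result would be biased. Step 1 shows otherwise: the stated power is delivered, and only a possible gain is forgone.

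A reader might also infer that the recorded measures are strong predictors. The documents do not show this. No section says how well they predict the composite in Section 5.4 (first intubation time over 60 seconds, first-attempt failure, or a provider rating of 4 or 5). Section 3.3 speaks of risk with conventional means, and Section 2.2 presents the flexible scope as useful where standard methods fail, including limited mouth opening. Difficulty with conventional methods need not carry over to these techniques.

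Selection weakens prediction further. Anyone with fewer than three criteria must have had radiation, so the two covariates are inversely related. In a simulation with each criterion independently present in 25% of the source population and radiation in 10% or 30%, their correlation among enrolled patients was about −0.6 to −0.7. Odds ratios as large as 2.0 per criterion and 2.7 for radiation gave an AUC of only 0.64 to 0.67, and the covariates themselves added 0 to 3.2 points. This makes the lower half of the range the safer expectation. It does not remove the point, because irradiated patients may enter with any count and some spread remains.

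Part of an apparent gain can also come from replacing the pooled chi-square by an unpooled Wald test: 1.0 to 1.3 points with no covariates at all. With the small-sample correction that artefact disappears (79.4% for both tests at AUC 0.50).

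Finally, it would be too strong to say that the plan allows no adjusted estimate of the primary outcome. Section 10.3 allows one, but names no covariates.

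**Conclusion.** The point holds as an efficiency and prespecification improvement. The planned test is sound and keeps its 80%, while information already collected goes unused in the main comparison. The expected benefit is about 0 points of power if the measures do not predict the outcome, 1.5 to 3 points at control-arm AUC 0.61 to 0.68 and about 6 points at 0.75, with standard errors about 0 to 8% smaller. These figures rest on the plan's 30% and 10% rates, 60 evaluable patients per arm, and assumed values for prognostic strength and for the mix of entry routes, none of which the documents supply.

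The improvement is worth making because exact power is 80.2%, with almost no margin, and Section 10.2 needs a primary-analysis paragraph anyway. Naming the exact test there matters at least as much: a move to Fisher or Yates would cost about 7 points (80.2 − 73.0 = 7.2), more than the adjustment is likely to gain.

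**What to change.** Add a primary-analysis paragraph to Section 10.2 before any outcome data are examined by arm:

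- The primary analysis is a covariate-adjusted risk difference. Fit a logistic regression on arm plus two covariates fixed in advance: the number of the seven difficult-airway criteria met, and history of head or neck radiation (yes/no). Standardise the predicted risks over the whole trial sample.
- Report a robust 95% confidence interval with a degrees-of-freedom-corrected variance and a t reference. This also supplies a between-arm interval, which the plan does not promise.
- Keep the chi-square test without continuity correction as the supporting analysis, and as the fallback if the model does not converge.
- Leave the 80% power statement in Section 10.1 as it is, for the unadjusted test.
- State in Section 10.3 that any other adjusted model of the primary outcome is exploratory.

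The cost is one paragraph and a little programming, with no extra patients. Section 5.3 does not list the individual airway items, so confirm that the case report form captures all seven criteria for patients who enter by radiation history; their eligibility does not depend on the count.

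The downsides are small. About 24 expected events limit the model to these two covariates. The gain may be nil if they do not predict difficulty with these techniques. Type I error may sit a few tenths of a point above 5%, as it does for the chi-square.

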## **10.2 Planned Statistical Analysis**

For the Secondary Objective:

To evaluate ease of use, each of the 3 dimensions described below will be assessed independently. First, the time of intubation will be assessed for distributional assumptions using histograms, stem and leaf plots, and box plots. Descriptive statistics such as the median and range or the geometric mean  $\pm$  SD will be used to summarize the data. Second, ordinal data describing the number of attempts will be summarized using the median and range; and third, the number of complications will be summarized using the median and range. For number attempts and complications, frequencies and percentages will be used if the maximum number is small ( $\leq$  4 attempts or complications). Comparisons between continuous covariates of interest will be conducted using a t-test, or Wilcoxon rank-sum test if more appropriate. Categorical covariates will be compared using chi-square or Fisher's exact test.

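### The number of complications has no assigned test and, once tabulated, may be compared by one that ignores order; Section 10.3 openly allows this for the Total Score

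*Combined protocol and SAP*

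**What the plan says.** Section 10.2 evaluates ease of use through intubation time, number of attempts and number of complications, each assessed on its own. By default "the number of complications will be summarized using the median and range". The summary changes with the data: "For number attempts and complications, frequencies and percentages will be used if the maximum number is small", with small defined as 4 or fewer.

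Two sentences on comparisons follow. Continuous covariates get a t-test, or Wilcoxon if more appropriate. For the rest, "Categorical covariates will be compared using chi-square or Fisher's exact test". No sentence says which of the two covers the number of complications, and no ordered or trend test is named for categorical data. The Brief Analysis Plan in the Summary Table repeats this text.

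Section 10.3 covers the 0 to 3 Total Score and the 1 to 5 rating of ease of ETT insertion. These outcomes are to be "compared between treatment arms using an independent samples t-tests or chi-square tests". It gives no rule for choosing between the two tests.

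**The concern.** A count of 0, 1, 2, 3 or 4 complications is ordered. A Pearson chi-square or Fisher test on the full table treats the values as unordered labels and spreads a consistent shift towards fewer complications over up to 4 degrees of freedom. An analyst told to tabulate the count may well reach for the categorical sentence, and may do otherwise if one patient has 5 complications. The Total Score raises the same issue more directly, because chi-square is expressly permitted.

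At stake is the chance of detecting a real reduction in complications, which Section 2.6 offers as part of the expected patient benefit, and whether the test is fixed before the data are seen. The number of attempts is not a concern: Section 5.2 allows at most two with the allocated technique, and on a two-level variable the tests practically coincide.

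**Working it through.** **Inputs.** Section 10.1: "A total of 60 evaluable patients will be randomized to each intervention arm", so n = 60 per arm. The test level comes from "a 2-sided chi-square test with alpha = 0.05"; it is stated for the primary outcome and assumed here for the others. The documents give no complication rate, distribution or power, and do not say which events make up the count. Every distribution below is therefore an assumption.

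**The plan's own power figure.** For 30% v 10%, the pooled rate is 0.20.
- Standard error under no difference: √(2 × 0.20 × 0.80 / 60) = 0.07303.
- Standard error under the alternative: √((0.30 × 0.70 + 0.10 × 0.90) / 60) = 0.07071.
- Power: Φ[(0.20 − 1.96 × 0.07303) / 0.07071] = Φ(0.804) = 78.9%. Exact binomial enumeration gives 80.2%.

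The stated 80% reproduces. It concerns the primary outcome only.

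**Tests compared.** Let a and b be the numbers of patients in a category in each arm, t = a + b, and N = 120.
- Pearson: X² = Σ(a − b)² / t, with degrees of freedom one fewer than the occupied categories.
- Wilcoxon, tie-corrected: W = Σ a × mid-rank, with mean n(N + 1)/2 and variance (n²/12)[(N + 1) − Σ(t³ − t)/(N(N − 1))]. The squared standardised W has 1 degree of freedom.

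**Complications, values 0 to 4** (20,000 simulated trials per row; Poisson values above 4 placed at 4):

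| Control v intervention | Chi-square | Wilcoxon | Loss (points) |
|---|---|---|---|
| Poisson mean 1.0 v 0.5 | 67.8% | 85.9% | 18 |
| Poisson mean 1.0 v 0.55 | 54.8% | 76.2% | 21 |
| Poisson mean 1.5 v 1.0 | 43.1% | 65.4% | 22 |
| Poisson mean 0.5 v 0.2 | 60.6% | 77.2% | 17 |
| .50/.25/.15/.07/.03 v .70/.18/.08/.03/.01 | 41.3% | 65.2% | 24 |
| Rare: Poisson mean 0.4 v 0.1 | 81.7% | 91.5% | 10 |
| Small effect: 1.0 v 0.8 | 9.9% | 19.5% | 10 |
| Large effect: 1.0 v 0.3 | 98.2% | 99.6% | 1 |

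**Smaller maxima** (means 1.0 v 0.5, 0.5 v 0.2 and 1.5 v 0.9). The loss is 12 to 15 points with a maximum of 3, 6 to 9 with 2, and essentially none with 1.

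**Fisher's test extended to more than two categories (Fisher-Freeman-Halton)**, 1,500 trials, values 0 to 4:
- 1.0 v 0.5: 85.9 − 70.7 = 15 points.
- 1.0 v 0.55: 76.2 − 58.3 = 18 points.
- 0.5 v 0.2: 77.2 − 65.7 = 11.5 points.

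**Analytic check.** A noncentrality that gives 80% power on 1 degree of freedom gives 70.9% on 2, 64.5% on 3 and 59.5% on 4. These are losses of about 9, 15 and 20 points, which agrees with the simulations.

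**Dependence on the largest value.** With Poisson means 1.0 and 0.5, the chance that one patient has 5 or more is 0.00366 and 0.00017. The chance that at least one of 120 does is 1 − (0.99634)^60 × (0.99983)^60 ≈ 21%. In that setting about one trial in five would fall on the other side of the threshold.

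**Total Score.** Assumed control distributions for scores 0 to 3 were .45/.25/.20/.10, .30/.30/.25/.15 and .60/.20/.12/.08, with proportional odds ratios of 2, 2.5 and 3. Chi-square power is 28% to 77% and Wilcoxon 43% to 90%, a gap of 12 to 19 points. The t-test is within about 0 to 5 points of Wilcoxon.

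**The case against.** The strongest reply is that the switch sentence governs description only. Nothing in Section 10.2 makes the summary format choose the test, and Wilcoxon is named in the same paragraph. That is correct. A reader might infer that the plan sends the count to chi-square or Fisher; the documents do not say so. What they show is that the test is unassigned and that an unordered one is an open reading.

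A reader might also take 17 to 24 points as the cost of the plan. That range needs Pearson chi-square, a moderate one-directional effect and counts spread over 0 to 4. In such sparse tables an analyst would often use Fisher instead: 94% to 99% of simulated trials, in four Poisson scenarios with raw gaps of 18 to 24 points, had an expected cell below 5. Part of the gap also reflects conservatism of chi-square in sparse tables. With equal means it rejected 3.4% to 4.0% of the time, against 5.4% to 5.6% for Wilcoxon (simulation error about 0.4 points). Setting both to 5% reduces those four gaps to about 12 to 17 points. This qualifies the size but does not remove the loss.

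In Section 10.3 the t-test is listed first and already uses the order, so the weakness there is the unrestricted choice. The Total Score's own split of complications into any v none suits a chi-square and is not in question.

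Finally, an unordered test is better when the difference is not in one direction. For .60/.10/.10/.10/.10 v .50/.40/.08/.01/.01, chi-square has 98.4% power and Wilcoxon 6.5%. That is a real trade-off, but the plan's hypothesis is a shift towards less harm.

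**Conclusion.** The point holds in a limited form. The number of complications has no assigned test, its handling may turn on the observed maximum, and the only tests named for categorical data ignore order. Section 10.3 permits an order-ignoring test for an ordered score without a rule for choosing it.

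With 60 per arm, two-sided 0.05 and a one-directional shift, the loss against Wilcoxon for complications runs from about 0 to 24 points: the upper end for Pearson chi-square on counts spread over 0 to 4, and nothing when the maximum is 1. For the Total Score it is material only if chi-square is picked. All of this rests on assumed distributions.

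It would be wrong to infer that planned power is lost. No power is stated for either outcome, one is secondary and the other exploratory, and the primary comparison and its 80% are untouched. This is an inexpensive improvement to supporting analyses.

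**What to change.** - **Section 10.2 and the Summary Table:** state that frequencies and percentages are for description only, and that the number of complications is compared between arms by the Wilcoxon rank-sum test whatever the observed maximum.
- **Section 10.3 and the Summary Table:** replace the open choice of t-test or chi-square for the Total Score with one order-respecting test, the Wilcoxon rank-sum.
- **Elsewhere:** keep chi-square or Fisher for binary or unordered outcomes, such as intubation failure and desaturation.

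The cost is about two sentences of wording, with no new patients, data or procedures. The small downside is lower sensitivity to non-monotone differences, which the frequency tables would still display.
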